11.5.7 Pharmacokinetic Analyses

Bioanalytical analysis of patient PK samples will be conducted at a centralized laboratory using validated assays. Plasma concentrations of doxorubicin and doxorubicinol will be summarized by descriptive statistics, including mean, standard deviation, coefficient of variation, minimum, maximum, and median. Data collected will be analyzed using a population pharmacokinetic approach.

Prior to analysis of the plasma samples, the presence of any microspheres in the plasma will be noted and it will be determined whether these spheres contain doxorubicin as this could impact the true assessment of the amount of doxorubicin circulating at the time the sample was taken.

The relationship between PK results and patient outcomes will be assessed for all patients with PK data on an exploratory basis. The correlation between circulating levels of doxorubicin and overall survival, tumor response, and doxorubicin related adverse events will be evaluated to the extent possible with the available PK data.

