As noted above, transarterial chemoembolization localizes the chemotherapy delivery to the tumor and creates ischemia of the lesion by occlusion of the feeding artery. Drug eluting chemoembolization advances that concept. In conventional chemoembolization the chemotherapy is mixed with ethiodized oil to help retain it in the tumor vasculature longer, and then the embolic agent acts as a plug. However the occlusion is limited in area and some of the drug still escapes into the peripheral circulation, which leads to adverse effects, as does the ethiodized oil to some extent. HepaSphere/QuadraSphere Microspheres add two benefits to embolization therapy. First, by ionically binding the doxorubicin throughout the microspheres (which have a slight negative charge that binds the positively charged doxorubicin), and eluting it in a controlled manner, more drug can be delivered into the tumor, with less escape into peripheral circulation. Complimentary to the sustained elution, HepaSphere/QuadraSphere Microspheres are also highly compressible and conformable, so they mould to the vessel lumen, creating both excellent contact with the intima for doxorubicin delivery and very efficient occlusion.

A bench study demonstrating proof of concept of consistent and efficient loading and elution of doxorubicin by these microspheres was presented by Liu (Cardiovascular and Interventional Radiology Society of Europe, Lisbon, Portugal, Sept 2009. Manuscript in preparation). [name] and colleagues experimented with multiple variations of loading methods, exploring different methods of solubilizing the doxorubicin (sterile water, normal saline, etc) and exposing it to microspheres under various conditions (dry, prehydrated with saline, prehydrated with non ionic contrast, etc) to determine the optimal method for uptake and release, as well as catheter patency.

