Four animal studies were conducted with HepaSphere/QuadraSphere: 2 to evaluate properties of the embolic itself without drug, and 2 to investigate behavior with doxorubicin. Khankan and colleagues (Khankan 2004) examined the effects of the superabsorbent polymer relative to a non drug eluting spherical embolic and particle PVA in a rabbit renal model. They determined that renal artery occlusion and coagulative necrosis occurred regardless of agent, but HepaSphere/QuadraSphere could achieve cross-sectional vessel occlusion distally with a single sphere and conformed to the lumen better than the other spherical embolic. Similarly de Luis (de Luis 2007)

observed in vivo size, deformation, final location and properties of HepaSphere/QuadraSphere in pig kidneys. The conclusion was that the embolic is stable, occludes perfectly, and morphologically adapts to the vessel lumen. The results of these two studies demonstrate the excellent ability of HepaSphere/QuadraSphere to block arterial blood supply and induce ischemia.

The other two animal investigations (VX-2 model in rabbits) have demonstrated feasibility and effectiveness of HepaSphere/QuadraSphere as a drug eluting embolic in vivo. Lee (2010) compared embolization using HepaSphere/QuadraSphere alone to embolization using the microspheres loaded with doxorubicin. They found that at 7 days, the bland embolic produced 60% cell death, but when loaded with doxorubicin, it resulted in 90% necrosis. The second study, by Gupta (SIR Mar 2008. Manuscript in preparation) evaluated conventional TACE to drug eluting HepaSphere/QuadraSphere, with the same dosage of doxorubicin in both arms of the study. Pharmacokinetic assays showed much lower C_{max} and AUC for doxorubicin in the drug eluting arm compared to the conventional TACE cohort. In addition, histopathological evaluation demonstrated that the doxorubicin levels in the tumors of the animals treated with conventional embolization was sparse, whereas it extended out as far as 1600 microns at 24 hours in the lesions of rabbits that were embolized with drug loaded HepaSphere/QuadraSphere, and was still detectable at 14 days.

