The first clinical data using HepaSphere/QuadraSphere was reported by Osuga and colleagues (Osuga 2002). In this study 6 patients with large liver tumors underwent bland embolization (no doxorubicin), and 2 of them had surgery afterward. In follow up, tumors were found to have varying degrees of necrosis, from partial to complete. Histologic examination showed that the embolic occluded intratumoral vessels tightly without ischemic damage to normal tissue. Post procedural pain was minimal, and no deterioration of liver function occurred. The same author also published a larger study of 59 patients treated for hepatocellular cancer with bland HepaSphere/QuadraSphere (Osuga 2008). There were no major complications and objective response rate by mRECIST criteria was 66%, but the authors found there was a high incidence of converting patients to drug eluting chemoembolization for future treatments due to progression after bland embolization.

Two recent Phase II clinical trials have demonstrated effectiveness of HepaSphere/QuadraSphere to deliver doxorubicin in patients with hepatocellular cancer. A multisite, open label investigation in Italy (Grosso 2008) evaluated 50 patients who had a maximum of 4 hepatocellular lesions each, treated with up to 3 chemoembolizations, using a dose of 50 mg of doxorubicin or epirubicin. The objective response using mRECIST criteria at 6 months was 77%. There were no major periprocedural complications. More recently van Malenstein and colleagues presented

the initial results from a single site clinical trial in Belgium (International Liver Cancer Association, Milan, Italy, Sept 2009. Manuscript in preparation). This prospective, randomized and controlled study of 30 patients compared conventional TACE to drug eluting HepaSphere/QuadraSphere. Patients received up to 3 embolizations, with a dosage of 50-75 mg/m² of doxorubicin. Pharmacokinetic studies demonstrated a significant difference in peak and overall circulating doxorubicin between the two cohorts. The effect of the larger amount of doxorubicin in the peripheral circulation of the patients who received conventional TACE was evident in the adverse events. There were 20 grade 3 (n = 12) or grade 4 (n = 8) adverse events among the patients who received cTACE compared with no grade 4 and only 4 grade 3 events in the HepaSphere/QuadraSphere group.

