 - iii. 20% decline from any value at screening
 2. Neutropenia
 3. Alopecia
 4. Hyperpigmentation
 5. Mucositis
- iii. Evaluate Resource Utilization as assessed by:
 1. Length of stay in hospital following each TACE procedure
 2. Number of unscheduled hospitalizations
 3. Length of stay of unscheduled hospitalizations
 4. New or increased use of non-OTC pain medications
 5. New or increased use of antibiotic medications
- iv. Evaluate overall adverse event rates between the treatment groups
- v. Evaluate objective response rates as determined by mRECIST criteria in the treated area (ORR-T)
 1. In this evaluation progression is defined as new/continued tumor growth in the treated area(s) of the liver or extrahepatic spread. New

tumor growth within an area of the liver not previously treated will not be considered progression.

c. Tertiary Objectives

1. Evaluate Time to Untreatable Progression defined as hepatocellular cancer for which further localized treatment by resection, percutaneous ablation, or embolization is not an option, or when there is extrahepatic spread of the cancer

Untreatable progression will be determined by the Central Reviewers during the study treatment and protocol-specified treatment follow up visits. After the final study TACE and associated assessments, untreatable progression will be determined by the treating physician during survival surveillance

2. Explore the relationship between pharmacokinetic (PK) data and patient outcomes including survival, tumor response, and adverse events

3. Inclusion Criteria

Patients must meet all of the following inclusion criteria in order to be entered into the study:

- a. Age 18 or older
- b. Patient has signed informed consent
- c. Patient must have a diagnosis of hepatocellular cancer confirmed by at least one of the following:
 - i. Histological confirmation
 - ii. Magnetic resonance imaging (MRI) result with early enhancement and delayed enhancement washout of at least one solid liver lesion > 1 cm. Patient must also have evidence of cirrhosis or have chronic hepatitis B.
 - iii. Contrast enhanced computed tomography (CT) with early enhancement and delayed enhancement washout of at least one solid liver lesion > 1cm. Patient must also have evidence of cirrhosis or have chronic hepatitis B.
- d. Patient must not be suitable for treatment by resection or percutaneous ablation at time of study entry.

Patients not suitable for ablation due to lesion location may be enrolled

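### Section 11.5.7 gives the PK-outcome correlations no treatment-arm term, so a correlation pooled over arms could not separate the arm effect from an exposure-response relation

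*Combined protocol and SAP*

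**What the plan says.** The tertiary objectives (section 2c) include: "Explore the relationship between pharmacokinetic (PK) data and patient outcomes including survival, tumor response, and adverse events". Section 11.5.7 carries this out in two sentences. The first sets the population and status: "The relationship between PK results and patient outcomes will be assessed for all patients with PK data on an exploratory basis". The second names the method: "The correlation between circulating levels of doxorubicin and overall survival, tumor response, and doxorubicin related adverse events will be evaluated", as far as the available data allow. The same section says "Data collected will be analyzed using a population pharmacokinetic approach", but it lists no covariates and does not say that model-derived exposure feeds the outcome correlations. No exposure metric, regression model, stratification or arm term is given.

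The background (section 1c) says how arm should affect exposure. With the microspheres, "more drug can be delivered into the tumor, with less escape into peripheral circulation". In rabbits given the same dose, the result was "much lower C_{max} and AUC for doxorubicin in the drug eluting arm compared to the conventional TACE cohort". In a 30-patient randomized human study, "Pharmacokinetic studies demonstrated a significant difference in peak and overall circulating doxorubicin between the two cohorts". No size or SD is given for the human difference.

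Section 11.2 assumes that arm also changes the primary outcome: median survival of 16 months on cTACE and 24 months on hqTACE.

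**The concern.** On the protocol's own expectations, treatment arm is a common cause of plasma doxorubicin and of outcome. If levels and outcomes from both arms go into one correlation without arm, part of what comes out is the between-arm contrast.

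The problem is sharpest for survival and tumor response. The device is meant to put more drug in the tumor and less in the circulation, so plasma level is not the intended route of benefit. If hqTACE prolongs survival, higher plasma levels would appear harmful in the pooled data even if, within each arm, level and survival were unrelated.

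Adverse events are different. The background attributes the excess toxicity of cTACE to circulating drug. If that is the only route by which arm affects toxicity, the between-arm contrast is legitimate exposure-response information. Whether it is the only route can be judged only from an analysis that includes arm.

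At stake is the reading of one tertiary objective. No primary or secondary result depends on it.

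**Working it through.** **The plan's own figure.** Section 11.5.7 states no number. The survival illustration uses the plan's event count, so that comes first. For hazard ratio 1.5, two-sided 5% and 85% power, the Schoenfeld formula gives 4 × (1.960 + 1.036)² / (ln 1.5)² = 218.4. This agrees with the 218 deaths in section 11.5.1.

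**Inputs from the documents.** 255 patients per arm; medians 16 and 24 months (hazard ratio 1.5); 218 deaths.

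**Assumptions not in the documents.** Log plasma doxorubicin is lower on hqTACE by d within-arm SDs, with d from 0 to 2. Within arm, level and survival are unrelated. All patients have PK data. Accrual is uniform over 36 months. The PK-survival analysis is done at 218 deaths.

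**Survival, closed form.** The expected log-rank Z for arm is ln 1.5 × √218 / 2 = 0.4055 × 7.382 = 2.99. The correlation between plasma level and arm is ρ = (d/2) / √(1 + d²/4). With no within-arm relation, the pooled test has expected Z of about 2.99 × ρ. The chance of p < 0.05 is then 1 − Φ(1.96 − 2.99ρ) plus the small opposite tail.

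**Survival, simulation.** 400 trials per setting (Monte Carlo standard error at most √(0.25/400) = 0.025), with Cox models on plasma level, pooled and stratified by arm.

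| d | ρ | Closed form, pooled | Simulated, pooled | Simulated, stratified | Pooled HR per SD |
|---|---|---|---|---|---|
| 0 | 0 | 5% | 5.5% | 5.5% | 1.00 |
| 0.5 | 0.243 | 11% | 10% | 5.8% | 1.05 |
| 1 | 0.447 | 27% | 27% | 4.0% | 1.08 |
| 1.5 | 0.600 | 43% | 41% | 5.0% | 1.10 |
| 2 | 0.707 | 56% | 56% | 5.5% | 1.11 |

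The two calculations agree, and the closed form does not use the accrual assumption.

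**Incomplete PK data.** If only 70% of patients contribute (borrowing the 30% non-evaluable rate of section 11.2), the deaths fall to 0.7 × 218 = 152.6. The arm Z becomes 0.4055 × √152.6 / 2 = 2.50. The closed-form rates become 9%, 20%, 32% and 43% for d = 0.5, 1, 1.5 and 2.

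**Binary outcome, no within-arm relation.** With assumed event rates of 20% and 40%, r = 0.25 × d × 0.2 / (√(1 + d²/4) × √(0.3 × 0.7)).
- d = 1: r = 0.098, p = 0.03 at n = 510, but p = 0.054 at n = 392 (2 × 196).
- d = 2: r = 0.154, p = 0.0005 at n = 510.

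**Adverse events, real within-arm relation.** Logistic models were simulated with a true odds ratio of 1.49 per SD and d from 1 to 2.

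| Direct effect of hqTACE on log-odds | Pooled OR | Arm-adjusted OR |
|---|---|---|
| None (arm acts only through plasma level) | 1.49–1.51 | 1.48–1.49 |
| −0.8 | 1.73–1.81 | 1.49–1.50 |
| +0.8 | 1.20–1.26 | 1.49–1.51 |

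The arm-adjusted estimate is right in all three cases. The pooled one is right only in the first.

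**The case against.** The strongest reply is that 11.5.7 does not prescribe an unadjusted pooled model. A reader might infer that it does from "will be assessed for all patients with PK data on an exploratory basis", but those words define a population. The section is silent on arm and excludes neither a by-arm nor an arm-adjusted analysis. This stands, so the point is an unaddressed term and not a stated wrong method. The plan does name treatment group explicitly in its poolability models (sections 11.5.1 and 11.5.2), so the omission is worth closing.

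A reader might also infer that a pooled correlation merely restates the arm effect. It does not. It mixes between-arm and within-arm information, and for adverse events it is unbiased if arm works only through plasma level, as the background suggests.

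The size is also open to challenge. The human study gives no SD and describes peak and overall exposure. This trial samples the morning after embolization, again 6 to 8 hours later only in patients not yet discharged, and at the first follow-up MRI (section 7.2; Appendix A, schedule footnote 9). The separation between arms at those times is unknown. This stands too, which is why a range is shown. At a small shift or with missing samples, the inflation is modest.

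Varying time from embolization to sample is partly met by the planned population PK approach, although the plan does not link that model to the outcome correlations.

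Finally, the analysis is labelled exploratory. That limits the consequences but does not remove the confounding.

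**Conclusion.** The point holds as a cheap improvement to a tertiary exploratory analysis. Arm is not addressed in 11.5.7, and the protocol expects it to change both plasma doxorubicin and survival. A pooled correlation therefore cannot distinguish an arm effect from exposure-response for survival or tumor response. For adverse events it can do so only if arm acts solely through plasma level.

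The size is a false-positive rate of about 10% to 56% for the pooled survival test, against about 5% with stratification. This rests on a plasma shift of 0.5 to 2 SD, complete PK data, uniform 36-month accrual, no within-arm relation and the plan's assumed survival effect. With no shift, or no effect of arm on survival, the inflation disappears.

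A reader might go on to infer that the result would be offered as proof of how the device works. Nothing in the documents says so, and the significance rule in section 11.1 is written for treatment comparisons.

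**What to change.** Add to section 11.5.7:
- Each PK-outcome relation is estimated within arm, or in a model with treatment arm and an arm-by-exposure interaction.
- The arm-adjusted coefficient is reported as the exposure-response result. Any correlation pooled over arms is labelled descriptive.
- The exposure measure and the sample it comes from are named.
- The model adjusts for time from embolization to sample where that time is captured, or uses exposure from the planned population PK model. The documents give a 6 to 8 am sampling window but do not say that actual draw times are recorded, so this should be confirmed.

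The cost is a few lines of text, one or two more model terms and slightly lower precision. No visit or sample is added, and treatment arm is known for every randomized patient.

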11.6 Safety Analysis

All safety analyses will be performed for the Safety Population on the locked database that will be unblinded only after all patients have completed the protocol specified treatment phase of the investigation.

11.6.1 Adverse Events

Safety summaries will include the incidence of treatment-emergent adverse events (TEAEs). Treatment-emergent adverse events (TEAEs) are defined as any event that began on or after the date of the first embolization or worsened in severity or frequency after embolization was initiated. Events worsening in severity should be considered new adverse events. Adverse events recorded on the CRF which began prior to treatment will not be included in the summary tables but will be included in the AE data listings.

All TEAEs will be coded using the Medical Dictionary for Regulatory Activities (MedDRA) and summaries will present data for both treatment groups by System Organ Class (SOC) and Preferred Term. TEAEs will be evaluated for severity using the CTCAE when available.

All TEAE summaries will be based on the number of patients experiencing an event, not the number of AEs experienced. For example, if a patient reports the same AE on 3 separate occasions that patient will be counted only once for that preferred term. Patients reporting more than one AE in a SOC will be counted only once in the SOC total. The denominator used for calculation of the percentages will be the number of patients in the Safety population in each treatment group.

Separate summaries will be generated for the following types of TEAEs:

- Overall TEAEs
- Severe TEAEs (grade 3 or higher)
- TEAEs related to doxorubicin specifically and treatment in general
- Serious adverse events (SAEs)
- Serious adverse events related to treatment
- TEAEs resulting in death

Treatment groups will be compared on the overall adverse event rates, and the rates of doxorubicin related adverse events during the protocol specified treatment phase of the investigation using Fisher's Exact Test.

The comparison of doxorubicin related adverse events will include:

- Clinically significant decline in left ventricular ejection fraction
- Neutropenia
- Alopecia
- Hyperpigmentation
- Mucositis

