The inclusion criteria for the currently proposed clinical trial are in part derived from results of a Phase II multisite clinical trial of a different drug eluting embolic (DC Bead, BioCompatibles, England). That investigation (Lammer 2009) included 201 patients who received up to 3 embolizations, with a dosage of doxorubicin up to 150mg each time. The patients were randomized to receive either conventional chemoembolization or drug eluting embolization using the DC Bead product. The primary objective was objective response at 6 months using mRECIST criteria, but the study did not meet its endpoint (p=0.11). However, in the subset of patients with more advanced disease, that is, those who had ECOG performance levels of 1 (rather than 0), recurrent or bilobar disease, or were Child-Pugh B (rather than A), the difference in response between the conventional and drug eluting arms was statistically significant. It was determined that the reason for this difference was that individuals with greater underlying liver disease or generally poorer hepatic status were able to tolerate embolization better when the drug release was controlled by the embolic (Lencioni, International Liver Cancer Association, Milan, Italy, Sept 2009). With these results in mind, we have focused the inclusion criteria for this proposed study on those patients most likely to derive the greatest benefit from treatment with HepaSphere/QuadraSphere.

2. Study Objectives

The objectives of this prospective, randomized, blinded and controlled clinical trial are as follows:

a. Primary Objective

- i. Evaluate overall survival in patients treated with doxorubicin delivery by HepaSphere/QuadraSphere compared to conventional transarterial chemoembolization with doxorubicin, lipiodol, and particle PVA

b. Secondary Objectives

- i. Evaluate overall objective response rates (ORR) determined by mRECIST criteria (Llovet 2008; Lencioni 2010) of hepatocellular carcinomas treated with doxorubicin delivery by HepaSphere/QuadraSphere compared to conventional transarterial chemoembolization with doxorubicin, lipiodol, and particle PVA
- ii. Evaluate doxorubicin related adverse events in patients treated with doxorubicin delivery by HepaSphere/QuadraSphere compared to those treated with conventional chemoembolization with doxorubicin, lipiodol, and particle PVA
 1. Decline in left ventricular ejection fraction
 - i. 10% decline from screening to below 50%
 - ii. Absolute value of 45% or less

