7.3 MRI and Laboratory evaluations following First TACE Cycle

MRIs of the liver, chest and pelvis and laboratory evaluations must be done within 4 weeks (± 1 week) of the first TACE cycle. If the patient received chemoembolization for bilobar disease, the MRIs and laboratory tests must be done within 4 weeks (± 1 week) of the embolization of the second lobe.

Laboratory evaluations will include those listed under screening, at a minimum, and results will be reviewed by the investigator and clinically significant changes from baseline will be reported as adverse events. Additionally, blood samples will be drawn for PK analysis. MRI results of the liver will be reviewed by Central Reviewers. If the patient has experienced a cardiac related adverse event, cardiac ejection fraction testing will be done.

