If a patient is withdrawn or discontinued from the study, the reason for withdrawal from the study will be recorded in the source documents and on the Study Termination CRF. All patients withdrawn from the study should be encouraged to complete, if possible, all clinical evaluations scheduled for the final visit. All adverse events should be followed as described in Section 9. The patient will be asked to give consent for survival follow-up contacts to be performed. Patients who are withdrawn from the study for any reason will not be replaced.

The study may be discontinued if, in the opinion of the Sponsor and/or the Data Safety Monitoring Board (DSMB), there is a significant risk to patients as evidenced by higher than anticipated adverse event rates, concern regarding unexpected serious adverse events, or device failures resulting in adverse events.

8. Adverse Events

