11.2 Sample Size Calculations

The sample size calculation for the primary efficacy analysis of the comparison of median overall survival between the two groups is based on the assumption of a 16 month median survival in the cTACE group and a 24 month median survival in the hqTACE group. A sample size of 196 patients per treatment group will have 85% power to detect this difference in median survival (Hazard ratio= 1.500) based on a 2-sided Type I error rate of 5%. Assuming a 30% non-evaluable rate, a total of 255 patients will be enrolled and randomized into each treatment group.

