11.3 Analysis Populations

11.3.1 Safety Population (SAF)

All randomized patients who have at least one TACE procedure will be included in the Safety Population.

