11.6.7 Cardiac Ejection Fraction (%)

Cardiac ejection fraction data will be collected at screening, after the second TACE, and at the final study visit for all patients. Cardiac ejection fraction testing will also be collected at additional time points during the protocol specified treatment phase of the investigation if the patient has experienced a cardiac related adverse event. Abnormal findings will be reported as adverse events. A summary table will be created summarizing the number and percent of patients having a clinically significant cardiac ejection fraction finding at each time point for each treatment group. This data will be presented in the data listings.

12 Data Safety Monitoring Board

A Data Safety Monitoring Board will be formed consisting of at least 3 individuals with expertise and experience in clinical trials, liver cancer and safety evaluations, but without direct involvement in the conduct of the study. The exact responsibilities, procedures, and guidelines used to manage the DSMB are described in a separate charter.

13 Records and Confidentiality

Each patient will be identified by study number only in the trial records. Study data will be recorded on pre-printed CRFs. Monitoring of study data recorded on the CRFs to source documents will be conducted for all patients to ensure accuracy and completeness.

14 Quality Control and Assurance

This study will be initiated and conducted under the sponsorship of BioSphere Medical, Inc., a wholly owned subsidiary of Merit Medical Inc. BioSphere Medical will supply pre-printed CRFs to all sites. Representatives of BioSphere Medical will monitor the study to verify study data, medical records, and CRF data in accordance with current ICH, GCPs and other applicable regulations and guidelines.

15 Good Clinical Practice

The study will be conducted in accordance with the International Conference on Harmonization (ICH) E6 for Good Clinical Practice (GCP): Consolidated Guidance and the appropriate regulatory requirement(s). The investigators will be thoroughly familiar with the appropriate use of the treatment procedure as described in the protocol. Essential clinical documents will be maintained to demonstrate the validity of the study and the integrity of the data collected. Master files should be established at the beginning of the study, maintained for the duration of the trial and retained according to the appropriate regulations.

16 Ethical Considerations

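### LVEF decline is seen only in patients who are re-tested, yet untested patients stay in the denominator as event-free; numbers tested and both denominators should be reported by arm

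*Combined protocol and SAP*

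**What the plan says.** Section 2.b.ii lists LVEF decline first among the doxorubicin-related events to be compared. It is defined by measured values: "10% decline from screening to below 50" per cent, an absolute value of 45% or less, or a 20% decline from any screening value.

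Section 11.6.1 includes "Clinically significant decline in left ventricular ejection fraction" among the events compared by Fisher's exact test, and says of the summaries: "The denominator used for calculation of the percentages will be the number of patients in the Safety population in each treatment group". Section 11.6 puts all safety analyses on the Safety Population, which section 11.3.1 defines without reference to testing: "All randomized patients who have at least one TACE procedure will be included in the Safety Population".

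On timing, section 11.6.7 says: "Cardiac ejection fraction data will be collected at screening, after the second TACE, and at the final study visit for all patients". Section 7.5 places the middle test at the evaluation after cycle 2. After cycle 1, section 7.3 provides: "If the patient has experienced a cardiac related adverse event, cardiac ejection fraction testing will be done". Section 7.8 requires a test at the visit that follows the final study MRI, whichever cycle was the last. For patients who leave, the Withdrawal of Patients section says: "All patients withdrawn from the study should be encouraged to complete, if possible, all clinical evaluations scheduled for the final visit".

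No rule covers a Safety patient with no post-baseline LVEF. Section 11.5.2, by contrast, states how patients without a post-baseline tumor evaluation are counted for ORR. Section 11.6.7 adds a table of LVEF findings by time point but does not give its denominator.

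**The concern.** An all-treated denominator is normal for events that patients or investigators notice and report, such as alopecia or mucositis. LVEF decline as defined here needs a test. A treated patient with no test after cycle 2, none at the final visit and none prompted by a cardiac event cannot be recorded as having a decline, yet adds one to the denominator. The effect is to impute no event for a missing measurement.

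Each arm's observed rate is then too low by the declines that went unmeasured. If the untested share also differs between arms, the comparison is distorted. The trial is built on an expected difference in survival, and death is one route to being untested, so equal losses cannot be assumed.

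**Working it through.** **Inputs from the plan.** Medians of 16 months (cTACE) and 24 months (hqTACE), from section 11.2: "16 month median survival in the cTACE group and a 24 month median survival in the hqTACE group". Randomized number 255 per arm (11.2), taken here as the Safety number. Two-sided 5% level (11.1). Visit intervals from sections 7.2 to 7.5.

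**Assumptions, not in the plan.** Exponential survival; true LVEF decline rates of 10% cTACE and 5% hqTACE; deaths as the only untested patients; the same decline risk in tested and untested patients.

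**Check of the plan's own figures.** The documents give no figure for the LVEF comparison. The survival assumptions behind this illustration do reproduce the plan's event count: 4 × (1.960 + 1.036)² / (ln 1.5)² = 218.4, against 218 deaths in section 11.5.1. Summing the visit intervals reproduces the response-assessment windows in the Treatment and Assessment section: unilobar 6+6+3 = 15 to 10+10+5 = 25 weeks; bilobar 3+6+3+6+3+3 = 24 to 5+10+5+10+5+5 = 40 weeks.

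**First routine post-baseline LVEF.** Unilobar: 8+4 = 12 weeks (range 9 to 15). Bilobar: 4+8+4+4 = 20 weeks (range 15 to 25).

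**Share dead by then.** 1 − 2^(−t/median), with t = weeks × 7/30.4375 months.
- Week 12 (t = 2.76): 11.3% cTACE, 7.7% hqTACE, about 29 v 20 of 255.
- Week 20 (t = 4.60): 18.1% v 12.4%, about 46 v 32 of 255.
- Over all permitted windows (weeks 9 to 25): 8.6–22.0% v 5.8–15.3%.

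**Observed rate = true rate × (1 − untested share).** Fisher power is by exact enumeration.

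| Timing | Observed rates | Difference | Ratio | Power, all Safety | Power, tested only |
|---|---|---|---|---|---|
| No loss | 10.0% v 5.0% | 5.0 | 2.00 | 52.2% | 52.2% |
| Week 12 | 8.9% v 4.6% | 4.3 | 1.92 | 42.5% | 48.8% |
| Week 20 | 8.2% v 4.4% | 3.8 | 1.87 | 36.6% | 47.6% |

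The difference is 15% lower at week 12 and 24% lower at week 20. At assumed rates of 15% v 7.5%, power on all Safety patients against tested patients is 62.2% v 70.4% (week 12) and 54.9% v 68.1% (week 20).

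**Half the early hazard** (medians doubled for this step). Week 12: 5.8% v 3.9% dead, 9.42 − 4.80 = 4.6 points, about 8% lower. Week 20: 9.5% v 6.4% dead, 9.05 − 4.68 = 4.4 points, about 13% lower.

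**Direction.** The observed ratio is the true ratio × (1 − untested cTACE)/(1 − untested hqTACE).
- Equal loss, 20% in each arm: 8.0% v 4.0%. The ratio stays at 2.00 and power is 41.5% on either denominator, although the absolute difference falls to 4.0 points.
- More loss in hqTACE, 10% v 20%: 9.0% v 4.0%. The ratio rises to 2.25, with power 57.9% on all Safety patients against 47.2% on tested patients. The absolute difference stays at 5.0 points in this example, because 10% of 10% equals 20% of 5%. With still more loss in hqTACE it would exceed 5.0.
- No true difference, 10% in each arm, with the death shares above: the Fisher test rejects 3.7% (week 12) or 4.0% (week 20) of the time, still under 5%.

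**The case against.** Five points can be made on the other side.

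- **Testing is wider than the cycle-2 visit.** A reader might infer that before that visit only a cardiac event leads to a test. Section 7.8 does not support this: a patient stopped after cycle 1 has a final visit with an LVEF test, nominally at week 4+4 = 8 (unilobar) or 4+4+4 = 12 (bilobar). Withdrawn patients are encouraged to attend it, and the schedule's footnote 7 allows tests as clinically indicated. This stands. The gap is confined to patients who die or leave without any of these tests, and the documents give no basis for estimating how many leave that way.
- **Early deaths may be fewer.** Entry requires a life expectancy of at least 6 months, and weeks 12 and 20 both fall inside that period. The arm gap also needs the planned survival benefit to operate from the first embolization. This stands, and is why the half-hazard case is shown. Untested withdrawals would add to the loss.
- **Early deaths may not carry the full-course risk.** They had fewer cycles, and a patient who died without a decline is correctly counted as event-free. This stands against the size. At the assumed rates the hidden declines are about 3 v 1 patients (255 × 0.113 × 0.10 and 255 × 0.077 × 0.05), or 5 v 2 at bilobar timing.
- **A tested-only denominator has its own bias.** Early tests are prompted by cardiac events. Take cTACE at week 12 with a true rate of 10%, and let prompted tests find half the declines among early deaths and test nobody else. All Safety gives 8.87 + 0.565 = 9.4%; tested-only gives 9.435/(88.7 + 0.565) = 10.6%. If prompted tests find every such decline, all Safety is exact at 10.0% and tested-only gives 10/(88.7 + 1.13) = 11.1%. This stands, and rules out simply replacing one denominator with the other.
- **The table by time point covers part of this.** It would show LVEF findings by visit, but its denominator is unstated and it does not change the Fisher comparison.

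**Conclusion.** The gap is real but limited. Sections 11.3.1, 11.6 and 11.6.1 together score a treated patient with no post-baseline LVEF as having no decline, and nothing elsewhere in the plan corrects this. The observed rate in each arm is understated to the extent that untested patients had declines.

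A reader might infer that the comparison is necessarily pulled toward no difference. The documents do not establish that. On the ratio scale it shrinks only if the arm with the higher LVEF risk also has the larger untested share. That is the case under the planning medians if cTACE is the more cardiotoxic arm. The ratio is exaggerated if the other arm loses more, and hardly changes if losses are equal.

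The falls of 15% and 24%, or about 8% to 13% at half the early hazard, are illustrations. They rest on assumed decline rates, constant hazards and deaths as the only loss. The plan claims no power for this comparison, and the primary endpoint is untouched. This is a cheap improvement, worth considering before unblinding.

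**What to change.** In sections 11.6.1 and 11.6.7:

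- Report by arm the number of Safety patients with a screening LVEF and at least one post-baseline LVEF, and the number without, by reason (died, withdrawn, not done).
- Give the LVEF decline rate and the Fisher comparison twice: among tested patients and in all Safety patients.
- Use patients tested at that visit as the denominator of the table by time point.
- State that a difference between arms will be interpreted only if the two analyses agree.

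The cost is some wording, one extra analysis and one table row, with no new tests or visits. The downside is that the tested-only result relies on tested and untested patients being comparable, which is doubtful where a cardiac event prompted the test. That is the reason for showing both results beside the counts.
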